CRC prevalence in patients diagnosed with SPS is 15-35%, according to different studies, and the probability at 5 years of developing a CRC is around 1.3-1.9%. During surveillance, the incidence of advanced neoplasia (advanced adenoma or advanced serrated lesions) at 3 years is 13% for adenomas and 42 for serrated lesions. Risk factors for developing CRC and advanced neoplasia have been described in several studies. One of these factors is the SPS criteria 2, which has been demonstrated as a low risk of CRC and advanced neoplasia during surveillance of SPS patients. Detecting more than two sessile serrated lesions proximal to the splenic flexure, one sessile serrated lesion with high grade of dysplasia and the detection of advanced neoplasia in

previous colonoscopies, are all risk factors of developing advanced neoplasia during surveillance. A recent multicentre prospective study established SPS patient surveillance according to lesions detected at last colonoscopy. Individuals with at least one advanced adenoma, an advanced serrated lesion or more than 5 relevant lesions (sessile serrated lesions, adenomas of any size or hyperplastic polyps more than 5 mm) were followed at one year. Patients with no lesions mentioned before were followed at 2 years with colonoscopy. Advanced neoplasia incidence in 2 years recommendation surveillance was 15.6% compared with 24.4% in the 1 year recommendation surveillance. CRC cumulative 5 years incidence was 1.3%. Regarding SPS type, the 5 years advanced neoplasia incidence was lower for patients with SPS criteria III of 2010 (26%) than for patients diagnosed with criteria I (53%) or criteria I and III (59%). In this study patients starting their surveillance with clearing phase achieved (clear colon of all polyps  $\geq$ 5mm and all polyps with the optical aspect of adenoma, TSA or SSL) were at low risk of advanced neoplasia than patients without this phase achieve prior to study inclusion (HR: 0.64; p<0.047).

With all the above described, it can be define a SPS patient with low risk of advanced neoplasia during surveillance: those patients with clearing phase achieved and without any advanced lesion or less than 5 relevant lesions at last colonoscopy.

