## **METHODS**

This is a prospective, randomized (1:1) and multicenter study, in Spanish national hospitals, with SPS patients diagnosed according to the reviewed WHO criteria in 2019, in a surveillance program and who meet all the inclusion criteria and no exclusion criteria.

Inclusion criteria:

- Patients aged 18 years or older that fulfil WHO criteria 1 or 2 of SPS.
  - Criteria 1: any patient with  $\geq 5$  SL proximal to the rectum, all  $\geq 5$  mm in size, with at least 2  $\geq 10$  mm in size.
  - Criteria 2: any patient with  $>20$  SL of any size distributed throughout the colon, with  $\geq 5$  lesions proximal to the rectum.
- Patients with a previous complete colonoscopy with adequate bowel preparation and with all lesions  $>5$  mm been resected ("clearance colonoscopy"), after the diagnostic of SPS.
- Nor advanced adenoma or serrated lesions at prior colonoscopy, and also either more than 5 relevant lesion (adenoma, SSL or PH $>5$ mm) at prior colonoscopy.

Exclusion criteria:

- Patients with no informed consent or who do not agree to participate in the study.
- Patients with total or partial colectomy.
- Patients with other CCR predisposing syndromes with germinal mutation (Familial adenomatous polyposis, Lynch syndrome, Peutz-Jehgers syndrome, Cowden syndrome, Juvenile polyposis syndrome...).

- Patients with chronic inflammatory bowel disease.
- Patients with coagulation disorders.
- Fragmented lesion or submucosal invasive lesion at last colonoscopy.
- Inadequate colon preparation: any segment of the colon with <2 points in Boston Scale (BBPS).

Patients selected for the study will be randomised in two groups for the surveillance: group 1, surveillance with colonoscopy in two years; group 2, surveillance with colonoscopy in three years. Randomization will be done at the database program (RedCAP).

All colonoscopies will be performed with high definition (HD) system and it will be the choice of the endoscopist whether to use chromoendoscopy with indigo carmine or virtual chromoendoscopy. Protocol bowel preparation will be recommended by each centre. Sedation will be prescribed and decided by the endoscopist during the examination.

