## SAMPLE SIZE CALCULATION

This is a randomized controlled study for evaluating a non inferiority strategy in the surveillance of SPS patients, between colonoscopy in 2 years and colonoscopy in 3 years, with the incidence of advanced neoplasia as the principal aim of the study. In the study from the Netherlands, Bleijenberg and col., the incidence of advanced neoplasia in patients at 2 years surveillance was of 15%. The investigators assume an acceptable increase of advanced neoplasia at 3 years surveillance of 25%, so the margin for no inferiority is 10% between the two groups. Accepting the type I error with an unilateral contrast of 0.025, beta risk of 0.2 (power 80%) and considering a 10% of lost patients, 69 patients in each group (136 in total) are needed to detect significance differences between the two groups.

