## STUDY VARIABLES:

- Demographic variables: Hospital, identification number (number assigned to each hospital and consecutive number of each patient), date of birth, sex, SPS criteria (according to WHO classification and actualized in 2019: 1 or 2), date of the last colonoscopy, number and type of lesions resected at the last colonoscopy, number of previous colonoscopies, number of polyps removed so far (low risk, high risk and serrated lesions), colon surgery (yes/no) and type of surgery (right colectomy, left colectomy, low anterior resection, segmental colectomy or others), smoker (yes/no/prev).
- Variables of the procedure: date of the procedure, bowel preparation according to BBPS scale, study arm (Colonoscopy in 2 years/Colonoscopy in 3 years), number and description of lesions resected during the procedure describing its size, shape according to Paris classification, location of the lesions, distance to the anal margin. Inspection time in each exploration (with stopwatch and without counting the therapeutic moments). Complications during the procedure (bleeding, perforation or cardio-respiratory events).

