## STATISTICAL CONSIDERATIONS AND STATISTICAL ANALYSIS PLAN

Numeric variables will be collected as integer number; they will be presented as mean and standard deviation in case of a normal distribution and compared with a

Student's t test. Categorical variables will be collected associated with an integer starting from cero; they will be presented as frequencies and compared with the Chi Square test. The risk of advanced neoplasia or CRC after 2 year colonoscopy surveillance will be compared with the risk of advanced neoplasia and CRC after 3 year colonoscopy surveillance using logistical regression analysis and expressed as Odds Ratio (OR).

Risk factors identified previously will be assessed in univariate and multivariate Cox Regression analysis, adjusted by age, gender and smoking status). They will be presented as Hazard Ratio (HR) with 95% of confidence interval. Statistical analysis will be performed with SPSS software version 19.0 (SPSS Inc., Chicago, IL, USA).

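### The 2- v 3-year comparison is not adjusted for SPS criterion, a collected baseline predictor; prespecifying the adjustment is a small, free gain

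*Combined protocol and SAP*

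**What the plan says.** All references are to the combined protocol and SAP.

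- **Statistical Considerations and Statistical Analysis Plan.** The arms are compared "using logistical regression analysis and expressed as Odds Ratio (OR". No covariate is named. Age, gender and smoking enter only a separate Cox analysis of previously identified risk factors. SPS criterion could be among those factors, but that model is not the arm comparison.
- **Methods.** "Randomization will be done at the database program (RedCAP", with 1:1 allocation. No stratification factor is stated. Patients meeting WHO 2019 criterion 1 or criterion 2 are eligible.
- **Study Variables.** The baseline data include "SPS criteria (according to WHO classification and actualized in 2019: 1 or 2". No rule is given for a patient who meets both.
- **Scientific Background.** Criterion 2 is described as low risk. For the cited cohort the text reports that "the 5 years advanced neoplasia incidence was lower for patients with SPS criteria III of 2010 (26" per cent), against 53% with 2010 criterion I and 59% with I and III together.
- **Sample Size Calculation.** The design is non-inferiority, 69 patients per group including 10% loss, "so the margin for no inferiority is 10% between the two groups".

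**The concern.** The plan's own background presents SPS criterion as a predictor that roughly doubles the risk of the primary outcome. The value is known at baseline for every patient, yet neither the allocation nor the arm comparison uses it. In arms of about 60 patients, the share with criterion 1 can easily differ by several points between arms, and that difference carries into the observed difference in advanced neoplasia.

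Two things are at stake. One is a small loss of precision. The other is that, with nothing fixed in advance, the choice between an adjusted and an unadjusted result can be made after the data are seen, in a trial whose conclusion depends on one confidence limit against a margin.

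**Working it through.** **Inputs from the plan.** "Accepting the type I error with an unilateral contrast of 0.025"; "beta risk of 0.2 (power 80" per cent); "the incidence of advanced neoplasia in patients at 2 years surveillance was of 15" per cent; margin 10 points; 10% loss; 69 per group; 5-year risks of 26% v 53% or 59% by criterion.

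**Assumptions.** The documents do not give the share f of patients in criterion 1; 30-50% is used. They do not give risk by criterion at 2 or 3 years in the enrolled population; a constant hazard is used to convert the 5-year figures.

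**1. Evaluable patients per arm.** 69 × 0.9 = 62.1, so about 62. The 69 is reproduced only if the distance to the margin is taken as 20 points: 7.849 × (0.15×0.85 + 0.25×0.75)/0.20² = 61.8, rounded up to 62, and 62/0.9 = 68.9, rounded up to 69. Equal rates of 15% with a 10-point margin give 7.849 × 2 × 0.15×0.85/0.10² = 200.1, so 201 evaluable per arm (224 with loss). That is a separate issue; here 69 only sets n = 62.

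**2. Risk gap between criteria (26% v 53%).**
- 2 years: 1 − 0.74^(2/5) = 11.3%; 1 − 0.47^(2/5) = 26.1%; gap 14.7 points.
- 3 years: 1 − 0.74^(3/5) = 16.5%; 1 − 0.47^(3/5) = 36.4%; gap 19.9 points.
- Plausibility: with f = 30% the overall 2-year risk is 0.7 × 11.3 + 0.3 × 26.1 = 15.7%, close to the plan's 15%.

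**3. Chance imbalance in the criterion 1 share.** SD = √(2f(1−f)/62) = 8.2 points at f = 0.3 and 9.0 points at f = 0.5.

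**4. Shift in the observed risk difference, 95% limit = 1.96 × SD × gap.**

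| Gap used | 95% limit |
|---|---|
| 2-year gap in both arms (14.7 points) | 2.4 to 2.6 points |
| Each arm's own gap (mean of 14.7 and 19.9 = 17.3 points) | 2.8 to 3.1 points |
| Rescaled to 15% overall, hazard ratio ln 0.47/ln 0.74 = 2.51 (gap 14.1 points at f = 0.3, 12.0 at f = 0.5) | 2.1 to 2.3 points |

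Other inputs go higher: the unscaled 5-year gap of 27 points with f = 0.5 gives 1.96 × 0.090 × 27 = 4.8 points. None of these figures is a maximum.

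**5. Precision gained by adjusting (rescaled rates).** Share of variance explained = f(1−f) × gap²/(0.15×0.85).
- f = 0.3: 0.21 × 0.141²/0.1275 = 3.3%.
- f = 0.5: 0.25 × 0.120²/0.1275 = 2.8%.
- Unadjusted SE = √(2×0.15×0.85/62) = 6.4 points; adjusted SE = 6.4 × √(1 − 0.03) = 6.3 points, about 1.5% smaller.
- The evaluable number needed falls from 201 to 195-196 per arm.

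**6. Simulation (100,000 trials, 62 per arm, f = 0.5).** The unadjusted estimate was unbiased. The false-positive rate at the margin was 2.7% unadjusted and 2.9% stratified; power was 36% and 37%. The two estimates differed by 0.9 points on average.

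**The case against.** The strongest reply is that nothing is broken. Randomisation makes the unadjusted comparison unbiased, and its confidence interval already includes the variation that comes from chance imbalance. This stands. A reader might infer from the shift of 2-3 points that the planned analysis is biased, or that this error comes on top of the interval. The documents support neither: allocation is random and the simulation shows no bias.

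The prognostic figures are also borrowed. They are 5-year risks under the 2010 criteria, in a cohort that included patients not yet cleared. The trial enrols cleared patients without advanced lesions at the prior colonoscopy, under the 2019 criteria. This stands too, and the gap may be smaller in them.

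The sample size matters far more. At 62 per arm the 95% half-width is 1.96 × 6.4 = 12.6 points, and power for the margin is about 34%. At 201 per arm the shift computed with the 2-year gap falls to 1.3-1.4 points. This sets the priority low but does not remove the case for a change that costs nothing.

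Adding a term to the planned logistic model would also give a conditional odds ratio, which is non-collapsible and not on the scale of the margin. With about 0.15 × 62 = 9 events per arm, several covariates would be unwise. And patients meeting both criteria have no stated code. These are fair, and they are met by a risk-difference estimate, a single binary covariate and a one-line coding rule.

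**Conclusion.** The concern holds as a modest, low-priority improvement. The arm comparison ignores a baseline variable that is collected for everyone and that the plan's own background shows to be prognostic. Prespecified adjustment would recover about 3% of outcome variance, or 1.5% of the standard error, and would close off a choice of model after the data are seen.

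The shift of roughly 2-3 points rests on 62 evaluable patients per arm, 30-50% in criterion 1, a constant hazard, and risk contrasts carried over from a different population. A reader might infer that imbalance can move the result by at most a quarter of the margin. The documents give no such bound: the figure is a 95% limit under assumed inputs, and other inputs give more or less. Nor would adjustment rescue the trial's power, which moves from 36% to 37% in the simulation.

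**What to change.** In the statistical analysis section, prespecify that:

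- the primary risk difference (3-year minus 2-year arm) is adjusted for SPS criterion, coded as criterion 1 (including patients who meet both) v criterion 2 only;
- it is estimated by Mantel-Haenszel, or by a logistic model with arm and criterion standardised to a marginal risk difference;
- the upper limit of the two-sided 95% confidence interval is compared with the 10-point margin;
- the unadjusted risk difference is reported as a sensitivity analysis;
- a conditional adjusted odds ratio is not used to judge the margin.

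If randomisation has not started, SPS criterion may also serve as the single stratification factor.

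Cost: a short addition to the plan and one coding rule. No new data, visits or patients are needed.

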## **OBJECTIVES:**

Principal:

- Evaluate the incidence of CCR and advanced neoplasia in SPS patients with low risk factors of advanced neoplasia during surveillance.

Secondary:

- Compare the incidence of advanced neoplasia between patient surveillance with colonoscopy at 2 and 3 years.
- Describe low risk factors of advanced neoplasia in SPS patient in our environment.
- Identify a group of patients with SPS and low risk of advanced neoplasia.

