Data from all the resected and visualized lesions during the colonoscopy will be collected on the database. A pathologist familiarized with serrated lesions will be in charge of the sample analysis. Serrated lesions will be classified according to WHO criteria for serrated lesions. The investigators define “advanced adenoma” as adenomas  $\geq 10$  mm with villous histology and/or with high grade of dysplasia (HGD). We define “advanced SL” as any SL  $\geq 10$  mm and any SL with dysplasia. The investigators define “advanced neoplasia” as any CRC, any advanced adenoma or advanced SL.

Quality of bowel cleansing will be graded by each endoscopist following the Boston Bowel Preparation Scale. This scale evaluates each segment (ascending colon, transverse colon and descending colon) of the following form: 0 = segment of colon whose mucosa cannot be seen due to the existence of solid stools that cannot be eliminated; 1 = mucosa portion of a colonic segment that can be seen, but other areas of the colonic segment are not seen, either due to the presence of dirt, feces or opaque liquid; 2 = existence of small amount of dirt, small fragments of stool and / or opaque liquid, but the mucosa of the colonic segment can be seen well; 3 = all the mucosa of the colonic segment can be seen well without residual dirt, small traces of stool or opaque liquid. Patients with inadequate preparation (when in any segment the score is 0 or 1, or the total score is less than 6) will be excluded from the study.

During colonoscopy all complications as post-polypectomy bleeding, perforation or cardio-respiratory events will be registered. Those complications will be considered if surgery or hospital admission is required.

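### Cox regression for the risk factors does not fit an outcome normally seen once, at an arm-timed colonoscopy; the main cost is lost power in a secondary analysis

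*Combined protocol and SAP*

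**What the plan says.** The METHODS section randomises each patient to one surveillance interval: "group 1, surveillance with colonoscopy in two years; group 2, surveillance with colonoscopy in three years". Lesion data come from that examination: "Data from all the resected and visualized lesions during the colonoscopy will be collected on the database". No interim look and no later round is described for the outcome.

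STUDY VARIABLES lists two relevant dates, one at baseline ("date of the last colonoscopy, number and type of lesions resected at the last colonoscopy") and one at the study examination ("date of the procedure, bowel preparation according to BBPS scale"). It lists no date of onset.

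The statistical analysis plan compares the arms on advanced neoplasia or CRC "using logistical regression analysis and expressed as Odds Ratio (OR"). For the risk factors it changes model: "Risk factors identified previously will be assessed in univariate and multivariate Cox Regression analysis", adjusted for age, sex and smoking and reported as hazard ratios with 95% intervals. It does not define event time, time origin, time unit or the handling of ties.

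Two of the three secondary objectives depend on this analysis. One is "Describe low risk factors of advanced neoplasia in SPS patient in our environment"; the other is to identify a low-risk group.

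**The concern.** A Cox model needs the time at which the event occurred, or a time up to which the patient is known to be free of it. Here the only fact per patient is whether advanced neoplasia was present at the examination. A lesion found at three years may have arisen at any time since baseline. If the attendance date serves as the event time, 3-year-arm patients enter the year-2 risk set as event-free although nobody examined them then.

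At stake is the ability to find real risk factors, which bears on who is called low risk. Few events are expected, so power is scarce under any model, and the plan already uses a binary model for the same outcome in the arm comparison.

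**Working it through.** **Inputs.** The plan gives no figure for the risk-factor analysis. Its only computed figure is the sample size of 69 per group. The stated inputs do not reproduce it: with 15% in both arms, a 10-point margin, one-sided 0.025 and 80% power, (1.960 + 0.842)² × 2 × 0.15 × 0.85 / 0.10² = 200.1, so 201 per arm, or 224 after 10% loss. I use 69 only to set the number of evaluable patients the plan expects: 69 × 0.90 = 62 per arm, 124 in all. The 2-year risk is from the sample-size section: "the incidence of advanced neoplasia in patients at 2 years surveillance was of 15" per cent. Assumed, because the documents are silent: a binary factor in 50% of patients, true hazard ratio (HR) 2 or 3, constant hazard, visits spread around schedule with SD 0 to 3 months and unrelated to the factor.

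**Expected events.** 62 × 0.15 + 62 × (1 − 0.85^1.5) = 9.3 + 13.4 = 22.7.

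**What Cox estimates (HR 2, visits exactly on schedule, Breslow ties).** Let x be the 2-year event-free probability in non-carriers. Then (x + x²)/2 = 0.85, so x = 0.8964.

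| Visit | Risk, non-carriers | Risk, carriers | Risk ratio | Odds ratio |
|---|---|---|---|---|
| 2 years | 10.36% | 19.64% | 1.90 | 2.12 |
| 3 years | 15.13% | 27.97% | 1.85 | 2.18 |

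Each arm has 31 carriers and 31 non-carriers. Expected events are 6.09 + 8.67 = 14.76 in carriers and 3.21 + 4.69 = 7.90 in non-carriers. Every risk set is half carriers, so the Cox estimate is 14.76 / 7.90 = 1.87. This is a pooled risk ratio, not the onset HR of 2. The complementary log-log contrast, ln(1 − 0.1964) / ln(1 − 0.1036), returns 2.00 at either visit. A simulation with n = 40,000 agrees: Cox 1.85 to 1.86, complementary log-log 1.96 to 1.97.

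**Power at 62 per arm, unadjusted, HR 2** (4,000 trials per scenario, two-sided 5% Wald test; three values are SD 1, 2 and 3 months):

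| Time unit | Cox, Breslow (%) | Cox, Efron (%) | Complementary log-log (%) |
|---|---|---|---|
| Exact dates | 25.9 / 25.2 / 26.2 | same (no ties) | 32.0 / 32.7 / 33.4 |
| Whole months | 27.0 / 25.2 / 25.3 | 29.6 / 26.4 / 26.6 | 34.8 / 32.0 / 34.2 |
| Whole years | 24.7 / 25.3 / 25.0 | 31.3 / 31.0 / 30.6 | 32.6 / 32.8 / 32.5 |
| Exactly on schedule | 25.9 | 32.0 | 33.7 |

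At HR 3, Breslow gives 54.4 to 56.8% against 65.2 to 67.4%. The loss is 9 to 12 points, or 2 to 3 with Efron ties and whole years.

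**With the planned covariates** (SD 2 months, exact dates). At HR 2, three sets of runs gave losses of 5.8 points (28.5 against 34.3%), about 8 (29 against 37%) and 8.3. At HR 3 it was about 12 (56 against 68%). The median Cox HR at true HR 2 was 1.95 to 1.97, against 2.06 to 2.13 for complementary log-log. At 201 per arm the attenuation is visible again: 1.84 to 1.87 against 1.99 to 2.01.

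**Null.** Unadjusted rejection was 2.4 to 4.7% for Cox and 4.0 to 4.9% for complementary log-log. With covariates, one set of runs gave 3.1 to 5.6% for Cox; another gave 5.9% for Cox and 5.7% for complementary log-log.

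**Other inputs** (HR 2, SD 2 months). The Breslow loss was 7.9 to 8.2 points at 30% prevalence, 4.1 to 6.4 at 70%, 5.6 to 7.1 for Weibull shape 0.5 and 10.3 to 10.9 for shape 2. Efron with whole years stayed at 1.3 to 2.1 throughout. The complementary log-log median HR was 2.00 to 2.02, so it does not hinge on a strictly constant hazard.

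**The case against.** The best case for leaving the plan alone is that no conclusion moves much. The analysis is secondary, the arm comparison already uses logistic regression, and with about 23 events the 95% interval runs from the estimate divided by about 2.4 to the estimate multiplied by 2.4 under either model. In an unadjusted run at HR 2 with exact dates, Cox coverage was 94.3%; with covariates it was 95.1%, against 95.3% for complementary log-log. Cox also keeps the hazard-ratio scale of the evidence cited in the background. Simply defining Efron ties and whole-year times would recover most of the power.

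Much of this stands. It limits the point to power and under-specification in a secondary analysis. It does not make Cox the better choice. The tie method and time unit are left open, exact dates are collected, and with exact dates the loss remains under either tie method. Complementary log-log regression keeps the hazard ratio without coarsening the dates.

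A reader might infer that the reported hazard ratios will be visibly too small. At this sample size, with the planned covariates, they will not: small-sample bias away from 1 offsets the attenuation, and the median Cox estimate is as close to 2 as its replacement's. A reader might also infer false-positive risk factors. The null test is not inflated by the choice of Cox unless carriers attend systematically earlier or later, and the documents give no data on that.

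**Conclusion.** The point holds as a mismatch between model and data, and the plan should be changed. Its main consequence is a loss of about 6 to 9 points of power at HR 2 and 9 to 12 at HR 3 with exact dates, shrinking to 1 to 3 points with Efron ties and whole-year times. These sizes rest on 62 evaluable patients per arm, 15% risk at two years, 50% prevalence, constant hazard and visit SD up to 3 months. Over the other prevalences and hazard shapes tried at HR 2, the Breslow loss ran from 4.1 to 10.9 points. Power is low under every model, so the change recovers part of what is missing and does not make the analysis well powered. Attenuation is a property of unadjusted models and larger samples and should not be claimed as a visible bias here. The arm comparison is outside the point.

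**What to change.** In the statistical analysis plan, replace Cox for the risk factors with complementary log-log regression of advanced neoplasia at the surveillance colonoscopy. Use log(time from last colonoscopy to procedure) as offset, keep the planned adjustment for age, sex and smoking, and report hazard ratios with 95% intervals. State the time origin as the date of the last colonoscopy, the only baseline procedure date listed.

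If logistic regression is preferred, include either study arm or actual interval, not both: they are nearly collinear, and exactly so if visits fall on schedule. With both, plus the factor, age, sex and three-level smoking, there are seven slopes for about 23 events, and one such run rejected a true null in 6.6% of trials. Report odds ratios and note that they lie further from 1 than the hazard ratio (2.12 to 2.18 for a true HR of 2 in the table above; a median of 2.29 in that adjusted run).

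The cost is one or two sentences, with no new data, since both dates are already collected. The downside is that the offset assumes a roughly constant hazard. The analyst should confirm that the named software fits this link with an offset.
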